Confidentiality: Procedures to minimize risks to confidentiality include recording demographic and contact information on a separate form from the rest of the experimental data, storing in locked file cabinets all forms or records with information about a subject that would allow identification, and the use of unique subject identifier codes on all experimental research data forms and electronic data files. Any electronic data files that would allow subject identification will be password protected on a secure server at each site. Except for the consent form, all data transferred from the clinical sites to Schepens will be de-identified and will be transferred via a secure method. Any photographs taken of the subject to verify the position of the frame on the face will include only one eye and the position of the frame around that eye (i.e., the photo will be de-identified). Other facial features or the full face will not be photographed. Each site will be provided with a mobile phone to capture the photo. The phone will not be connected to any internet or mobile networks. The study personnel will transfer the photo to a PowerPoint slide with instructions to crop unnecessary identifiable information that may inadvertently be included in the photo and only save the cropped version. Each site will be provided with a laptop encrypted at MGB which will be used to run the software and log the data for the VR walking simulator test.

8. Benefits

Potential Benefits to Participants: Subjects will get to take home and try two pairs of prism glasses (retail cost of \$1000 or more for each). The glasses may help them to detect and avoid collisions with obstacles when walking resulting in safer mobility during everyday activities. At the end of the study, they may be allowed to keep one pair of glasses, if clinically appropriate, which may continue to help them in the longer term to detect obstacles when walking.

Potential Benefits to Society: Demonstrating efficacy of the MPP glasses will give patients with HH access to a new type of glasses having much better image quality and greater expanded field of view compared to those currently in the market. We expect that the use of these glasses will help patients with HH detect obstacles on their blind side and therefore aid safer mobility in everyday situations.

9. Statistical Analysis

Data analysis plan

The differences in blind-side detection improvement rates between MPPs and FPPs will be analyzed using a McNemar test for data combined across both periods of the crossover, testing the hypotheses that improvements rates will be higher with MPPs than with FPPs at the 40° bearing angle (primary hypothesis) but will not differ at 20° (secondary hypothesis). An intention to treat analysis will be used. Participants who withdraw after treatment allocation but before the end of the crossover will be categorized as no improvement for both types of prism glasses. Questionnaire responses will be analyzed with non-parametric statistics. An α -value ≤ 0.01 will be considered to indicate statistical significance for the primary analysis and ≤ 0.05 for the secondary analyses

Sample size estimate:

The sample size calculation is based on results from a small pilot study ($n = 6$) conducted in [name] lab at Schepens in which participants with hemianopia completed measurements of collision detection using the same test as in the clinical trial. The sample size is computed for the primary outcome based on a McNemar test for a 2-by-2 contingency table of the binary improvement (yes/no) for MPPs and FPPs for detection of 40° pedestrians with data combined across both periods of the crossover. In the lab-based pilot study, 100% of participants improved with MPPs for the 40° pedestrians and 33% improved with FPPs. For the clinical trial, we anticipate that some participants will not show improvement with MPPs, and the overall effect size will be smaller. We therefore estimate that 70% of participants will improve with MPPs and 25% will improve with FPPs. The minimum sample size to detect a 45% difference between the proportion of participants improving with MPPs and FPPs is 36 participants, assuming 20% overlap (i.e. improved with both MPPs and FPPs), power of 90% and significance (alpha) level of 1%, 2-tailed test. Allowing for 30% failing to meet inclusion criteria and 20% attrition after starting the clinical trial, we estimate a total sample size of 54 participants.

Based on prior multi-site clinical trials of prism glasses for HH ([name] et al., 2014), we expect that up to 30% of enrolled participants may fail to meet the inclusion criteria and 20% may withdraw after treatment allocation. Therefore, we will need to enroll at least 55 participants in total (as screening is done at the first visit). In addition, prior to the main clinical trial, we plan to conduct a pilot of the clinical trial at Schepens and Mass Eye and Ear to verify study procedures and generate data to verify the sample size calculation. We plan to enroll 10 participants for the pilot clinical trial. Therefore, the total enrollment will be 65 participants.

10. Monitoring and Quality Assurance

Adverse event criteria and reporting procedures

Criteria to define adverse events:

This protocol uses the definition of adverse event from 21 CFR 312.32 (a): any untoward medical occurrence associated with the use of an intervention in humans, ***whether or not considered intervention-related***.

- **Serious adverse event** means any event temporally associated with the subject's participation in research that meets any of the following criteria:
 - results in death;
 - is life threatening (places the subject at immediate risk of death from the event as it occurred);
 - requires inpatient hospitalization;
 - results in a persistent or significant disability/incapacity; or
 - any other adverse event that, based upon appropriate medical judgment, may jeopardize the subject's health and may require medical intervention to prevent one of the outcomes listed above.

Unanticipated Problems:

Any incident, experience, or outcome that meets all of the following criteria:

- It is unexpected (in terms of nature, severity (see severity grades below), or frequency) given (a) the research procedures that are described in the protocol-related documents, such as protocol and informed consent documents; and (b) the characteristics of the subject population being studied;
- It is related or possibly related to participation in the research (possibly related means there is a reasonable possibility that the incident, experience, or outcome may have been caused by the procedures involved in the research); and
- It suggests that the research places subjects or others at a greater risk of harm (including physical, psychological, economic, or social harm) than was previously known or recognized.

This definition could include an unanticipated adverse device effect, any serious adverse effect on health or safety or any life-threatening problem or death caused by, or associated with, a device, if that effect, problem, or death was not previously identified in nature, severity, or degree of incidence in the investigational plan or application (including a supplementary plan or application), or any other unanticipated serious problem associated with a device that relates to the rights, safety, or welfare of subjects (21 CFR 812.3(s)).

Reporting Adverse events:

All adverse events whether serious or non-serious, expected or unexpected, will be reported as soon as possible to the PI ([name]) or co-PI ([name]) - by a subject or member of the research team.

They will promptly review documented adverse events to determine 1) if the event should be classified as an adverse event; 2) if there is a reasonable possibility that the adverse event was caused by the study device(s); and 3) if the adverse event meets the criteria for a serious adverse event.

[name] (PI) and [name] (co-PI) will be responsible for determining whether an AE is expected or unexpected. An AE will be considered unexpected if the nature, severity, or frequency of the event is not consistent with the risk information previously described for the study device.

All AEs will have their relationship to the study device assessed. The PI will determine the AE's causality based on the temporal relationship and his/her best judgment. The degree of certainty about causality will be graded using the categories below.

- **Definitely Related** – There is clear evidence to suggest a causal relationship, and other possible contributing factors can be ruled out.
- **Possibly Related** – There is some evidence to suggest a causal relationship. However, other factors may have contributed to the event (e.g., the participant's clinical condition, other concomitant events).
- **Not Related** – There is no reasonable possibility that the study device caused the event, there is no temporal relationship between use of the study device and event onset, or an alternate etiology has been established.

The severity of a non-serious, unexpected adverse event will be graded as follows:

- **Mild adverse event** – Events that do not interfere with the participant's daily activities.
- **Moderate adverse event** – Events result in a low level of inconvenience or concern with the use of the glasses. Moderate events may cause some interference with regular activities related to mobility.
- **Severe adverse event** – Events interrupt a participant's usual daily activity but not potentially life-threatening or incapacitating. Of note, the term "severe" does not necessarily equate to "serious". (For example: A person suffering a temporarily incapacitating injury such as a sprained ankle due to slipping on snow while wearing the prism glasses, even though the fall was not caused due to wearing the glasses)

Any adverse events that are serious, unexpected and related or possibly related to the study will be reported to the Mass Eye and Ear IRB within 7 calendar days from the time the PI becomes aware of the event. Any unexpected and study-related death will be reported to the Mass Eye and Ear IRB within 24 hours of the PI's knowledge of the event by e-mail or telephone. If there is any doubt as to whether an incident or observation is an AE, the event will be reported to IRB nevertheless based on the schedule described below.

The PI will report events to the IRB based on the following schedule:

- Possibly, Probably, or Definitely Related Expected AE – Report to IRB on annual basis
- Possibly, Probably, or Definitely Related Expected Serious AE – Report to IRB within 7 days
- Possibly, Probably, or Definitely Related Unexpected AE – Report to IRB within 30 days of event
- Possibly, Probably, or Definitely Related Unanticipated Problem – Report to IRB within 7 days of event (24 hours for death or data loss)
- Possibly, Probably, or Definitely Related Unexpected Serious AE – Report to IRB within 7 days of event (24 hours for death)

Unanticipated Problem Reporting

All UAPs involving risks to subjects or others will be reported to the Mass Eye and Ear IRB within 7 calendar days from the time the PI becomes aware of the event. If a UAP or an unexpected Serious AE results in a subject's death or was potentially life-threatening, the PI will notify the Mass Eye and Ear IRB

through e-mail or phone within 24 hours from the time the event is identified. A follow-up report will be submitted if applicable, at a later date when more information is available. For UAPs that result in data loss the PI will notify the Mass Eye and Ear IRB through e-mail or phone within 24 hours from the time the UAP is identified.

Planned safety monitoring

The subjects in this study will not be participating in any activities that they would not otherwise participate in as a part of their daily life. The subjects are not expected to be exposed to any potential risks other than those commensurate with the fitting of prismatic devices in a regular low vision clinic. No irreversible effects of using prism glasses or effects related to the duration of use of the glasses have been reported in our experience so far. Given the minimal risk involved in participating in the study and the nature of the use of these glasses, the study will be primarily monitored for safety by the PI. An external safety monitor ([name], OD, PhD, MPH) will also be appointed. Schepens Eye Research Institute will act as the data and safety monitoring center for the study.

Monitoring for Off-site Adverse Events (Solicited and Unsolicited)

The subjects will be instructed to report any adverse events to the study personnel through telephone or email as soon as they occur (Unsolicited report). The study personnel will interview the subject for the occurrence of any adverse event while wearing the prism glasses at home during the telephone follow-up (One week after providing the glasses) or during the return visit to the clinic (After 4 weeks of using the glasses). Events reported by the subject during these interviews will be noted as solicited adverse events. Personnel preparing the study safety logs will screen for double reporting of solicited/unsolicited events.

Internal monitoring:

Study sites will submit source data and data collection sheets to Schepens by secure file transfer after each subject visit (please see Description of Data management methods below). Internal monitoring of the source data documentation, completion of data sheets, protocol adherence, recording keeping will be carried out weekly by a research assistant (or other study team member) at Schepens under the supervision of [name] (PI) and [name] (co-I). The research assistant will also note any documented AEs or UAPs. AEs or UAPs that occur on-site will be noted in the subject's data sheets. Additionally, a separate monitoring log of expected and unexpected events and any solicited or unsolicited AE report, will be kept and sent to the PI on a case-by-case basis (usually within 24 hours of the event occurrence). This monitoring log will be stored electronically. Non-compliance with protocol (e.g., failure to use the study checklist, complete data sheets correctly, or properly document or report in a timely manner adverse events) will be documented. Once identified, minor issues will be addressed by the PI by special meeting or at weekly study meetings. Special meetings may be called depending on the seriousness of the issue. Repeated offenses will result in removal of that study staff from the protocol. Adverse events will be documented and reported to the IRB and NEI per the schedule described in the protocol.

Outcomes monitoring, including planned frequency of review.

Data summaries will be produced by the research assistant (including data on topics such as subject enrollment, withdrawals, primary outcome measures, and any safety issues) and reviewed by the PI and other study personnel during weekly study meetings. Approximately once a quarter, data summaries will be reviewed by an internal committee comprising the PI and members of the research team at Schepens to monitor data quality, primary outcomes and study progress.

Internal Data Safety Monitoring Committee and External Safety Monitor

The PI will be the primary safety monitor for this study. An internal data safety monitoring committee consisting of the PI, co-investigator ([name]) and other members of the study team at Schepens will periodically review the study reports internally as mentioned above. Additionally, an external safety monitor, [name], OD, PhD, MPH, who has no conflict of interest with the study will be appointed (please see uploaded letter and CV). [name] is a clinician-scientist with specialist expertise in rehabilitation of patients with brain injuries and clinical trial experience. He will review safety monitoring reports prepared by the research assistant about twice a year. These reports will include data on aspects such as subject enrollment (numbers screened and enrolled), subject losses (numbers withdrawn or lost to follow up), data form completion, clinical outcomes (number of subjects advised to continue with the study devices, or to continue without devices after completion of the study), and any safety issues.

Study stopping rules as applicable

There are no study stopping rules (other than the criteria for terminating a subject from the study, detailed in the section on study termination criteria above)

Independent monitoring of source data as applicable:

Not applicable

Description of data management methods:

Data collection sheets will be completed for each subject enrolled into the study. Data collection sheets will be study visit specific and the study personnel preparing the weekly summaries for the PI will review the data sheets for completeness and document any minor protocol deviations.

Subjects will be identified by a unique study ID code that will be used on all data sheets and electronic data files. Links between study ID codes and subject identifiers will be kept in a separate secure document in a secure location at the site where the subject was recruited. The code that links information that can identify the participant to the data collected for this research will be kept separate from their health information and will be destroyed once this study is complete and all manuscripts have been published.

When study sites outside the MGB network are added to the protocol, personnel at the sites will scan de-identified datasheets and transfer them to Schepens using a secure file-sharing system that only the study team will have access to. Any deviations from protocol will be documented on a deviation log and communicated with the study site. All computer-generated data will be de-identified and shared using the approved file sharing system along with the data collection sheets. Only the PI and researchers specific to this study who have been granted access to the data by the PI will be able to view the data.

Originals of consent forms will be kept in a secure location at each site. Electronic scanned copies of consent forms, attested as true copies by study personnel, will be sent to Schepens by the secure transfer method.

11. Select the Privacy and Confidentiality measures that apply to this research:

- ☒ Study procedures will be conducted in a private setting
- ☒ Only data and/or specimens necessary for the conduct of the study will be collected

- ☒ Data collected (paper and/or electronic) will be maintained in a secure location with appropriate protections such as password protection, encryption, physical security measures (locked files/areas)
- ☒ Specimens collected will be maintained in a secure location with appropriate protections (e.g. locked storage spaces, laboratory areas)
- ☒ Data and specimens will only be shared with individuals who are members of the IRB-approved research team or approved for sharing as described in this IRB protocol
- ☒ Data and/or specimens requiring transportation from one location or electronic space to another will be transported only in a secure manner (e.g. encrypted files, password protection, using chain-of-custody procedures, etc.)
- ☒ All electronic communication with participants will comply with Mass General Brigham secure communication policies
- ☒ Identifiers will be coded or removed as soon as feasible and access to files linking identifiers with coded data or specimens will be limited to the minimal necessary members of the research team required to conduct the research
- ☒ All staff are trained on and will follow the Mass General Brigham policies and procedures for maintaining appropriate confidentiality of research data and specimens
- ☒ The PI will ensure that all staff implement and follow any Research Information Service Office (RISO) requirements for this research

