Subjects will use the first pair of prism glasses in everyday mobility as much as possible for about four weeks. They will receive a telephone call about one week after visit 2 to review how they are using the prism glasses, answer any questions they may have, and check for any adverse events that might have occurred.

- **Visit 3: Evaluation of performance with first pair of prism glasses and fitting second pair**

- Visual fields (without and with first pair of glasses)
- VR walking simulator test (without and with first pair of glasses, order counterbalanced)
- Mobility questionnaire and device questionnaire (for first pair of glasses)
- First pair of glasses will be retained at the study site
- Fit second pair of prism glasses
- Photo to document fitting of second pair of prism glasses (includes only the eye and frame on the side the prisms are fitted)
- Training in how to use second pair of glasses including a walk through corridors and rooms, accompanied by a member of the research team

- **Home use - second pair of prism glasses**

Subjects will use the second pair of prism glasses in everyday mobility as much as possible for about four weeks. They will receive a telephone call about one week after visit 3 to check that they are using the prism glasses, answer any questions they may have and check for any adverse events that might have occurred.

- **Visit 4: Evaluation of performance with second pair of prism glasses and clinical decision**

- Visual fields (without and with second pair of glasses)
- VR walking simulator test (without and with second pair of glasses, order counterbalanced)
- Mobility questionnaire and device questionnaire (for second pair of glasses)
- Comparison questionnaire (compare two pairs of prism glasses)
- Clinical decision by practitioner about whether subject should continue with MPP, FPP or no prisms (based on practitioner's clinical judgment, subject's preference and if performance with the prism glasses is not worse than the performance without the prism glasses during the study visits).

- **Optional extended wear with long term follow up**

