Subjects who have a clinical decision to continue and wish to continue with either the MPP or the FPP glasses will be invited to participate in the extended wear phase of the study. Participants in the extended wear phase will receive a follow up telephone call about 6 months after Visit 4 and again about 12 months after Visit 4 to determine whether they are still using the prism glasses. If a subject is having difficulties with the prism glasses during the extended wear phase, a study visit to review the problems will be arranged if necessary. Otherwise there will be no in-person study visits during the extended wear period.

If a subject is interested in continuing with prism glasses, but not willing to participate in the telephone follow ups, they will not be able to participate in the extended wear trial and the study team will retain both pairs of prism glasses. (They could, however, be fitted with prism glasses by their eye doctor outside of the study as part of clinical management of their condition). Based on

prior experience, we believe that it is highly unlikely that a subject who wants to continue with either the FPP or MPP glasses will not be willing to receive the follow-up phone calls. Completion of the extended wear part of the study is the best way for us to determine whether it is appropriate for the subject to continue to wear prism glasses in the long term.

We believe that this is in the participant's best interests. Based on prior experience of two multi-site trials of the FPP glasses for hemianopia, it is highly unlikely that a participant who wants to try the prism glasses in the longer term would not be willing to participate in the extended wear part of the study, which involves only 2 telephone calls.

There will be no long term follow up for subjects who do not have a clinical decision to continue with either the MPP or FPP glasses.

At the end of study participation, all subjects will return to the routine care of their eye doctor.

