Rationale for permitting subjects to keep glasses only after the end of the extended wear period: By the end of the crossover period, participants will only have worn each pair of prism glasses for 4 weeks. This is a relatively short period of time. It is long enough to evaluate whether it is clinically appropriate for them to continue with prism glasses in the extended wear phase of the study, but not long enough to determine whether they should continue with glasses in the long term. It is only after participants have worn prism glasses for an extended period (more than 4 weeks) that we will be able to fully determine whether they should continue to use glasses in the long term after the end of the extended wear part of the study. Therefore, participants will only be permitted to keep glasses after the end of the extended wear part of the study.

Table 1: Schedule of visits and assessments

	Visit 1	Visit 2 Day 1	1-week follow up Day 8 ± 3	Visit 3 Day 29 ± 7	1-week follow up Day 36 ± 3	Visit 4 Day 57 ± 7	6 month follow up Day 225 ± 21	1 year follow up Day 393 ± 21
Informed Consent	X							
Visual acuity	X							
Visual fields without prism glasses	X			X		X		
Visual fields with prism glasses				X		X		
Neglect tests	X							
Cognitive status test	X							
Ocular and other relevant history	X							
Ocular examination	X							
Refraction	X							
Binocular status tests	X							
Measurements for prisms with photo	X							
Fit and train in use of prism glasses		X		X				
Photo to document fitting of prisms		X		X				
VR walking simulator practice		X						

Mass General Brigham Institutional Review Board
Detailed Protocol

	Visit 1	Visit 2 Day 1	1-week follow up Day 8 ± 3	Visit 3 Day 29 ± 7	1-week follow up Day 36 ± 3	Visit 4 Day 57 ± 7	6 month follow up Day 225 ± 21	1 year follow up Day 393 ± 21
VR walking simulator data collection				X		X		
Mobility questionnaire		X		X		X		
Device questionnaire				X		X		
Comparison questionnaire						X		
Clinical decision on keeping glasses						X		
Telephone follow up			X		X		X	X

Data collection methods and variables

- **Clinical tests and questionnaires**

At each visit, results of clinical tests and responses to questionnaires will be recorded by study staff at each site on the relevant data collection sheets (included as attachments). Electronic scanned copies of the data sheets will subsequently be sent to Schepens by secure data transfer for review and analysis.

- **VR walking simulator**

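### The protocol provides for no solicited adverse event check after Visit 4: the 6- and 12-month extended-wear calls have continued use as their only stated purpose

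*Combined protocol and SAP*

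**What the plan says.** Four places bear on this.

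- **Section 6, Home use (first and second pair).** A call is made about a week after each fitting. Its stated tasks for the first pair include to "answer any questions they may have, and check for any adverse events that might have occurred". The call for the second pair carries the same check.
- **Section 6, Optional extended wear with long term follow up.** Participants who continue with either device are called about 6 months after Visit 4 and "again about 12 months after Visit 4 to determine whether they are still using the prism glasses". No other purpose is given. In-person visits are not planned unless a participant has trouble with the glasses.
- **Section 10, Monitoring for Off-site Adverse Events.** Staff interview participants about adverse events "during the telephone follow-up (One week after providing the glasses) or during the return visit to the clinic", the latter being the visit after four weeks of use. Events from these interviews are the ones classed as solicited. Separately, participants are told to report events themselves as they happen.
- **Section 6, rationale for when glasses may be kept.** Four weeks on each pair is described as too short to settle long-term use. Only after a longer period of wear, it says, "we will be able to fully determine whether they should continue to use glasses in the long term".

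Section 10, Planned safety monitoring, adds that neither irreversible effects nor "effects related to the duration of use of the glasses have been reported in our experience so far".

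**The concern.** The protocol gives extended wear a specific job: to show whether a participant should go on wearing prism glasses. That judgement depends on harms as well as on use. In a phase with no routine visits, the two calls are the only scheduled opportunity to ask about falls, collisions or discomfort, and the text does not say that anyone asks.

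Volunteered reporting generally finds fewer events than direct questioning, especially minor ones and those the participant does not link to the glasses. A low count after Visit 4 could therefore reflect the method of collection rather than the safety of long-term wear. The statement on duration of use reports past experience, and the multi-periscopic prism is the new device. Extended wear is where this trial could add evidence on the point.

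**Working it through.** The plan states no figure for this, so there is nothing to reproduce. The inputs are the target days and windows in Table 1 of section 6.

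**Inputs**
- First pair fitted: Visit 2, Day 1
- One-week calls: Day 8 and Day 36
- Visit 3: Day 29
- End of crossover: "Visit 4 Day 57 ± 7"
- First extended-wear call: "6 month follow up Day 225 ± 21"
- Last extended-wear call: "1 year follow up Day 393 ± 21"

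**Solicited contacts**
- Day 1 to Day 57: four (Days 8, 29, 36 and 57). The two calls rest on sections 6 and 10. The two visits rest on section 10 alone, because the visit lists in section 6 do not show an adverse event item.
- After Day 57: two calls, neither with a stated adverse event check.
- Table 1 has no adverse event row for any contact, so it does not settle the matter either way.

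**Share of scheduled wear without a solicited contact**

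Share = (last call day − Visit 4 day) / (last call day − Visit 2 day)

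- Target days: (393 − 57) / (393 − 1) = 336/392 = 85.7%
- Late Visit 4, early last call: (372 − 64) / (372 − 1) = 308/371 = 83.0%
- Early Visit 4, late last call: (414 − 50) / (414 − 1) = 364/413 = 88.1%
- Wear stops at the first extended-wear call: (225 − 57) / (225 − 1) = 168/224 = 75.0%
- The continued device only, 28 crossover days plus 336: 336/364 = 92.3%

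**If both calls solicited events**

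The recall intervals would be 225 − 57 = 168 days and 393 − 225 = 168 days, and no part of the 392 scheduled days would lie outside a solicited interval.

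**The case against.** The strongest counter-argument is that the text gives the purpose of the calls, not their script. The data collection sheets are attachments that are not part of the public document, and they may contain an adverse event item. Silence in section 6 is weak evidence by itself: the lists for Visits 3 and 4 are also silent, yet section 10 makes those visits solicited contacts. This stands as a limit on the claim. One cannot say that participants will not be asked, only that the protocol does not provide for it. But section 10 defines solicited events by the one-week call and the four-week visit, so if the forms do ask, the text still needs to say so.

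A reader might infer that there are no safety data after Visit 4. The documents do not support that. Self-reporting has no stated end, a review visit can be arranged for difficulties, and the termination criteria in section 6 (danger to the participant or others, a serious adverse event, risky behavior such as driving in the glasses) are not confined to the crossover.

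A reader might also infer that the decision on keeping the glasses rests on continued use alone. It does not. The Remuneration text makes it depend on clinical appropriateness, and volunteered events and review visits can inform it. Nor is the external safety monitor left out: the reports made about twice a year already cover any safety issues, without limit to a phase.

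Finally, extended wear is optional, the study is described as minimal risk, and no primary or secondary outcome comes from this phase. All of that is true and keeps the point modest. It does not explain why the question asked at one week should be left out of calls already scheduled at 6 and 12 months.

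**Conclusion.** The point holds as a gap in planned solicitation. With the protocol followed as written, about 86% of scheduled wear (336 of 392 days; 83% to 88% across the visit windows) has no solicited adverse event contact and relies on volunteered reports and reactive visits.

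This rests on two assumptions: that the unseen call forms add nothing to the stated purpose, and that the participant wears the glasses to the 12-month call. The share is 75% if wear stops at Day 225, and the figure does not apply to anyone who stops at Visit 4. It measures time, not events. To read it as the proportion of adverse events missed would go beyond the documents, which give no event rates.

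The efficacy analyses are untouched. The point is worth acting on because the protocol itself relies on this phase to judge long-term wear and because the correction is cheap.

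**What to change.** Amend two places so that they agree.

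- **Section 6, Optional extended wear:** state that the 6- and 12-month calls ask the same adverse event question as the one-week calls, covering any event since the last contact. Record which device is in use and, if wear has stopped, why.
- **Section 10, Monitoring for Off-site Adverse Events:** add both calls to the contacts at which events count as solicited.

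No new reporting route is needed. The events would enter the safety reports that already go to the external monitor and would be available when keeping the glasses is considered. If the call forms already carry the question, only the protocol text has to change.

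The cost is a few minutes per call, a line or two on the form and an IRB wording amendment. There are two downsides. Recall over about 168 days will be imperfect, particularly for minor events. Counts from this phase will not be directly comparable with those from the crossover, where contacts are far closer together, so the two should be tabulated separately.
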